#### 10. JUDGEMENT CRITERIA

#### 10.1. MAIN JUDGEMENT CRITERION

- The primary outcome measure will be the 16-week percent change since baseline of the severity score mTLSS (modified Total Lesion Symptom Score).
- The mTLSS combines an evaluation of hand eczema lesions severity including 6 key signs (erythema, desquamation, lichenification/hyperkeratosis, vesiculae, oedema, fissures) and the intensity of pruritus and pain.

#### 10.2. SECONDARY JUDGEMENT CRITERIA

- Evolution of pruritus associated with CHE at week 16 since baseline measured with a visual analog scale.
- Evolution of pain associated with CHE at week 16 since baseline measured with a visual analog scale.
- Improvement of quality of life at week 16 since baseline measured by DLQI (Dermatology Life Quality Index) and EQ-5D.
- Evolution of sleep loss associated with CHE at week 16 since baseline measured with a visual analog scale.
- Clearance or almost clearance of hand eczema at week 16 as defined by an Investigator's global assessment (IGA) of 0 or 1.
- Clearance or almost clearance of hand eczema at week 16 as assessed by the Patient's global assessment (PaGa) of 0 or 1.
- Improvement of work productivity at week 16 since baseline as assessed by the WPAI questionnaire (Work Productivity and Activity Impairment).
- Evolution of the Eczema Area and Severity Index at week 16 since baseline in patients who have eczema on other parts of the body than the hands.
- The safety throughout the course of the study (at 20 weeks since baseline) by monitoring adverse events, serious adverse events, injection site reactions.
- The evolution of laboratory parameters (full blood count, total IgE and specific IgE) at week 16 since baseline.

# 11. STUDY PROCEDURE

# 11.1. STUDY CALENDAR

The duration of the study for each patient will be between 21 and 24 weeks and will comprise three phases:

- A screening phase with a duration of 1 to 4 weeks
- A treatment phase with a duration of 16 weeks (4 treatment visits with injection, 4 self-injection at home or 4 injections at site by study staff and end of treatment visit)
- A post treatment follow-up phase with a duration of 4 weeks (follow up visit planned 6 weeks after the last injection and 4 weeks after the end of treatment visit)

The inclusion of the first patient happened in July 2019. The inclusion period is 54 months.

# 11.2. TABLE SUMMARISING PATIENT FOLLOW-UP

Phase	Screening	Treatment period								Follow up period	
Visit	Screening	V1	(V2)	V3	(V4)	V5	(V6)	V7	(V8)	V9	V10 FU Visit
Day/Week	Up to 4 weeks prior to Visit 1	Day 0	Week 2	Week 4	Week 6	Week 8	Week 10	Week 12	Week 14	Week 16	Week 20
Visit window (days)			±3	±3	±3	±3	±3	±3	±3	±3	±3
Informed consent	X										
Height and weight		X								X	
Demographics and characterisation of hand eczema	(X)	X									
Previous therapy for hand eczema	(X)	X									
In-/exclusion criteria	X										
Concurrent diagnoses	(X)	X									
Medical history	(X)	X									
Duration of hand eczema and other locations of eczema	(X)	X									
Other atopic comorbidities	(X)	X									
Concomitant medication	(X)	X		X		X		X		X	X
Physical examination	(X)	X									
Randomization		X									
Adverse Event(s)		X		X		X		X		X	X
AESI (Conjunctivitis)		X		X		X		X		X	X

# DUPECZEMAIN RC31/18/0269 - Version $n^{\circ}$ 6.0

Phase	Screening		Treatment period								Follow up period
Visit	Screening	V1	(V2)	V3	(V4)	V5	(V6)	V7	(V8)	V9	V10 FU Visit
Day/Week	Up to 4 weeks prior to Visit 1	Day 0	Week 2	Week 4	Week 6	Week 8	Week 10	Week 12	Week 14	Week 16	Week 20
Visit window (days)			±3	±3	±3	±3	±3	±3	±3	±3	±3
Laboratory – Biochemistry (fasting)		X								X	
Laboratory full blood count	X									X	
Laboratory screening for hepatitis B, C and HIV	X										
Laboratory including specific IgE dosage (only Toulouse site)		X								X	
Laboratory including Total IgE dosage		X								X	
Pregnancy test*	X	X		X		X		X		X	X
Vital signs (BP, pulse, temperature)		X									
Photographs		X				X				X	

Phase	Screening	Treatment period									
Visit	Screening	V1	(V2)	V3	(V4)	V5	(V6)	V7	(V8)	V9	v10 FU Visit
Day/Week	Up to 4 weeks prior to Visit 1	Day 0	Week 2	Week 4	Week 6	Week 8	Week 10	Week 12	Week 14	Week 16	Week 20
Visit window (days)			±3	±3	±3	±3	±3	±3	±3	±3	±3
Patients Global Assessment of disease severity		X		X		X		X		X	
Investigator's Global Assessment of disease severity		X		X		X		X		X	
EASI		X		X		X		X		X	
mTLSS		X		X		X		X		X	
Hand eczema pruritus by VAS		X		X		X		X		X	
Hand eczema Sleep loss by VAS		X		X		X		X		X	
Hand eczema Pain assessment by VAS		X		X		X		X		X	
DLQI		X		X		X		X		X	
EQ-5D-5L		X		X		X		X		X	
WPAI		X								X	
Skin Biopsy (sub study only)		X								X	
Removal of the stitches (sub study only)			X								
Blood sample for sub study		X								X	
Subject treatment instructions		X									
Study treatment administration		X	(X)	X	(X)	X	(X)	X	(X)		

\*Serum pregnancy test required at Screening visit and V9, urinary pregnancy test will be performed at V1, V3, 5, 7 and 10

Each visit will be conducted by the investigator (Dermatologist, Allergologist) at the dermatology outpatient clinic in the participating centers.

#### 11.3. SCREENING VISIT

The screening visit is conducted by the physician investigator. The screening visit will occur between 1 week and at the latest 4weeks before the inclusion visit. A screening assessment to determine study eligibility will be performed at this visit. Before any examination related to the study, the investigator will obtain the patient's informed, written and freely given consent (or if necessary that of his legal representative)

#### **OBTAINING CONSENT**

During the screening visit, the investigator provides the patient with information and answers all his or her questions about the objective, the nature of constraints, foreseeable risks and benefits expected from the study. He also explains the patient's rights in relation to a biomedical research study and checks his eligibility criteria. A copy of the Patient Information and Informed Consent form is then given to the patient by the investigator.

After this information meeting, the patient has a period of time to consider his decision. The investigating doctor is responsible for obtaining the patient's written informed consent. The consent form must be signed BEFORE ANY CLINICAL OR LABORATORY EXAMINATION NEEDED FOR THE STUDY IS PERFORMED.

If the patient agrees to participate, he and the investigator clearly write their last names and first names, date and sign the consent form.

The various copies of the Patient Information and Informed Consent form are then distributed as follows:

- A copy of the Patient Information and signed Informed Consent form is given to the patient.
- The original copy is kept by the investigating doctor (even if the patient moves house during the period of the study) in a safe place inaccessible to third parties.
- At the end of inclusions or at the latest at the end of the study, a copy of each Informed Consent form is sent to the sponsor or his representative using the methods communicated in due course to the investigators.

#### DEMOGRAPHICS AND CHARACTERISATION OF HAND ECZEMA

At this visit, characterization of hand eczema will be performed by the physician investigator including, occupation, personal history of atopic dermatitis (as defined by Williams Criteria: Williams HC, Burney PG, Pembroke AC, Hay RJ. Validation of the U.K. diagnostic criteria for atopic dermatitis in a population setting. U.K. Diagnostic Criteria for Atopic Dermatitis Working Party. Br J Dermatol 1996;135:12-7.), presence of atopic comorbidities including asthma, allergic rhinitis and allergic conjunctivitis.

Duration of hand eczema, presence and evaluation of eczema on other sites of the body will be recorded.

Previous therapy received for hand eczema (medication, duration of exposure) will be recorded.

#### LABORATORY TESTING

Bloods sample will be drawn for safety and IgE follow up. The total volume of blood for the study will not exceed 50 ml.

At screening visit will performed:

- o Full blood count including Eosinophils (EDTA tube 3ml) will be performed by site.
- Serum hCG for women of child-bearing potential (tube SST 3ml): a serum pregnancy test must be taken at the screening visit in female subjects of child-bearing potential. This test will be performed by site.
- Screening for hepatitis B, hepatitis C and HIV (2 SST tubes de 7 ml) will be performed by site.
   It includes hepatitis B virus surface antigen, virus surface antibody, and virus core antibody, hepatitis C virus antibody, HIV-1 and HIV-2 antibody.

# 11.4. BASELINE VISIT (V1)

At the inclusion visit V1 at day 0, the following procedures will be conducted by the investigator or designee:

#### RANDOMIZATION PROCEDURE

The investigator completes the "randomization" web page after previously confirming all the eligibility criteria of the patient on the site. After validating the content (and particularly, randomization stratification factors), inclusion takes place and the site immediately communicates to the investigator and to the pharmacy the patient's unique number in the study, the result of the randomization, in particular the number of the treatment box.

#### DEMOGRAPHICS AND CHARACTERISATION OF HAND ECZEMA

At this visit, characterization of hand eczema will be performed by the physician investigator including, occupation (aggravating factors due to work environment), aggravating domestic factors, personal history of atopy including atopic dermatitis (as defined by Williams Criteria: Williams HC, Burney PG, Pembroke AC, Hay RJ. Validation of the U.K. diagnostic criteria for atopic dermatitis in a population setting. U.K. Diagnostic Criteria for Atopic Dermatitis Working Party. Br J Dermatol 1996;135:12-7.), history of patch testing with results, history of prick tests with results, and food allergy.

#### LABORATORY TESTING

- Serum Chemistry (heparin tube 5 ml) will be performed by site. It includes: sodium, potassium, creatinine, urea mitogen, calcium, alkaline phosphatase, aspartate aminotransferase, GGT, alanine aminotransferase, bilirubin, lactate dehydrogenase, cholesterol, LDL, HDL, triglycerides, glucose (fasting) albumin, protein.
- o Total IgE will be performed by site
- Specific IgE (SST tube 3ml) will be performed for patients from Toulouse and Lyon sites, by the immunology laboratory Rangueil Hospital [name], France.
- o Urinary pregnancy test must be performed at baseline prior to randomization in female subjects of child-bearing potential.

# **WEIGHT AND HEIGHT**

The subject height must be measured (without shoes) and weight must be determined (in indoor clothing and without shoes)

#### CONCOMITANT MEDICATIONS / ADVERSE EVENT (AE)

Any medication or vaccine that subject receives from 3 months priori screening through safety follow up must be recorded in the subject's medical record and the eCRF along with the details such as: reason for use, dates of administration (start and stop date), dosage information (dose and frequency). Similarly, concomitant procedures must also be recorded in the subject's medical record and the eCRF.

AEs must be collected from time of first trial-related activity after the subject has signed the informed consent form until completion of the clinical trial. AEs must be assessed by medically qualified personnel. AEs reported by the subject or observed by the investigator must be recorded on the AE form of the CRF and should be described.

AESI (Conjunctivitis) must be recorded in the eCRF and reported immediately to the Sponsor (see.section 10.3).

#### **VITAL SIGNS**

Vital signs (resting blood pressure, pulse and body temperature) must be assessed according to the flowchart before randomization. Vital signs also should be done at 1 hour post-injection (+/- 10 minutes) at baseline visit.

Vital signs will be measured in sitting position following at least 5 minutes rest.

Clinically significant abnormal vital signs at the baseline visit will be documented as medical history in the eCRF. It will be up to the investigator's discretion if the subject should be randomized into the trial. If an abnormal vital signs at any other visit than baseline visit is considered by the investigator to be clinically significant, it will be reported as an AE in accordance with the principles for data entry.

In case of abnormal findings, the vital sign measurement can be repeated approximately 15 minutes later with the subjects resting in a sitting position to verify the first measurement.

PHOTOGRAPHS OF THE HANDS: photographs of palms and dorsal hands will be performed. The trial sites will use their own equipment to take the photographs. Instruction for photography will be provided to the site in a photography procedure. The photographs will have no other subject identifier than the subject ID and will be collected by CRA on USB device. Sponsor may at its discretion use the photographs in publications, posters and similar types of information material.

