- WPAI questionnaire: The work productivity and activity impairment questionnaire-atopic dermatitis (WPAI) records impairment due to CHE during the past 7 days. The WPAI-AD consists of 6 items grouped into 4 domains: absenteeism (work time missed), presenteeism (impairment at work/reduced on-the-job effectiveness), work productivity loss (overall work impairment/absenteeism plus presenteeism), and activity impairment. Scores are calculated as impairment percentages (28), with higher scores indicating greater impairment and less productivity.
- Perform randomization (for details see page 30) and give subject treatment instructions to the patient
- Administer study drug (sub cutaneous injection of the first dose of dupilumab or placebo): site staff will perform the first injection and will explain to patient how to perform self-injection and will stay with him for the first self injection (second injection)
- Monitor the patient for 1 hour after the SC injection: vital signs and AE assessment (for details see page 30) should be done at 1 hour post-injection (+/- 10 minutes). Injection site reaction (ISR) photograph will be taken, if applicable.

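### The vital-signs recording rule splits by visit rather than by first injection, so as written it sends the only scheduled post-dose reading to medical history and conflicts with AE collection at V1

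*Protocol*

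**What the plan says.** Section 11.4 (Vital signs) sets two readings at the baseline visit, V1. The first: "Vital signs (resting blood pressure, pulse and body temperature) must be assessed according to the flowchart before randomization". The second: "Vital signs also should be done at 1 hour post-injection (+/- 10 minutes) at baseline visit". An abnormal finding may be rechecked about 15 minutes later.

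The same section then says how abnormal findings are recorded. For V1: "Clinically significant abnormal vital signs at the baseline visit will be documented as medical history in the eCRF". The next sentence reads: "It will be up to the investigator's discretion if the subject should be randomized into the trial". For other visits, the AE rule begins: "If an abnormal vital signs at any other visit than baseline visit is considered by the investigator to be clinically significant", and such a finding is reported as an AE.

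The section 11.2 table has a row "Vital signs (BP, pulse, temperature") marked at V1 only. The visit descriptions in sections 11.5 and 11.6 list no vital signs.

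Other parts of the protocol ask for AEs on the same day:
- The AE row of the section 11.2 table is marked at V1.
- Section 11.4 (Concomitant medications / Adverse event) collects AEs from the first trial activity after consent, on the AE form.
- The closing steps of section 11.4 say "Monitor the patient for 1 hour after the SC injection" and pair vital signs with an AE assessment at that hour.
- Section 12.3 has AEs assessed at every evaluation time point, with causality judged by the investigator.

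**The concern.** Medical history describes the patient before treatment. A recording rule should therefore turn on whether the finding came before or after the first injection. This rule turns on which visit it was, and the first injection falls in the middle of that visit. A clinically significant change in blood pressure, pulse or temperature one hour after dosing meets the words of the medical-history rule and is excluded by the words of the AE rule.

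What is at stake is the completeness of the safety data. Sections 3.4 and 12.2 name hypersensitivity as a risk of dupilumab. Section 14 cites surveillance for injection reactions among its reasons for having no independent monitoring committee. Comparing safety with placebo is a secondary objective (section 4.2). A finding held only as medical history would not reach the causality assessment in section 12.3 or the AE tables in section 13.4, assuming those tables are built from the AE form.

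**Working it through.** No figure in the plan needs reproducing and no rate is given, so the check is a count of readings and a comparison of rules.

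**Scheduled vital-sign readings per patient** (sections 11.2 and 11.4)
- V1 before randomisation: 1
- V1 one hour after injection: 1
- V3, V5, V7, V9 and V10: 0
- V2, V4, V6 and V8 (injection only): 0

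Total = 1 + 1 + 0 + 0 = 2, of which 1 is post-dose.

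**Each rule applied to each reading**

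| Reading | Timing | Medical-history rule (baseline visit) | AE rule (any other visit) |
|---|---|---|---|
| V1, first | before randomisation | applies | excluded |
| V1, second | 1 hour after injection | applies as written | excluded as written |
| Unscheduled, later visit | after dosing | excluded | applies |

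The AE rule therefore covers 0 of the 2 scheduled readings. It can be reached only if a site happens to measure vital signs at a later visit. The medical-history rule covers both, including the single scheduled post-dose reading.

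**Is the second reading really at the baseline visit?** Yes. The sentence that schedules it says so, in the same section as the recording rule. No exemption is given there or elsewhere.

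**Do the other sections give the same instruction?** No. For a clinically significant abnormality at the one-hour check, the recording rule says medical history. The V1 mark in the AE row, the AE collection window, the paired AE assessment and section 12.3 all point to the AE form. The exceptions to collection in section 12.3 cover certain hospital admissions, not vital signs. Nothing says which instruction prevails, so sites may differ.

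**What could be lost?** Section 12.3 requires a serious event after consent to be notified on the day the investigator learns of it, wherever the reading is entered. What remains exposed is a non-serious, clinically significant vital-sign abnormality at one hour. Injection site reactions and other clinical signs fall outside the sentence.

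**The case against.** The strongest reply is that context settles the meaning. The sentence after the rule leaves randomisation to the investigator, which makes sense only for a reading taken before randomisation. The section also opens with that reading. This is persuasive about intent, and the fault is most likely one of drafting. It does not cure the text, because the rule is worded for the whole visit and the post-injection reading is expressly placed in that visit.

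The second reply is that AE recording on Day 0 is already mandatory. Section 12.1 defines an AE broadly, the passages listed above require it to be recorded, and nothing says that a medical-history entry replaces an AE entry. This stands in part: a site could, and perhaps would, record the event as an AE. Misfiling is what the rule prescribes if read alone. It is not a certain result.

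A reader might infer three stronger things that the documents do not support:
- *That acute reactions to the first dose are in fact being recorded as pre-existing conditions.* The other AE provisions stand against this, and nothing in the protocol shows any misfiled case.
- *That the error favours dupilumab.* The rule applies to both blinded arms. A directional effect would need more post-dose vital-sign abnormalities on dupilumab than on placebo, and the protocol gives no rate for either arm. Section 13.4 plans no between-group test of AE incidence.
- *That all 94 planned patients are affected.* That figure would count scheduled readings, not misfiled findings. Only clinically significant abnormal one-hour readings matter, and only at sites that follow this rule over the others.

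A delay in reporting serious reactions does not follow either, since the notification duty in section 12.3 rests on seriousness.

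**Conclusion.** The point holds as an internal contradiction in a recording rule, with limited severity. As written, the section 11.4 vital-signs rule classifies the only scheduled post-dose reading as medical history, against the AE collection required at V1 by sections 11.2, 11.4 and 12.3. A site that follows it could leave a post-dose abnormality out of the treatment-emergent AE tables in section 13.4.

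The reach is 1 of 2 scheduled readings per patient and, within that, only non-serious abnormalities judged clinically significant. The number of events cannot be derived from the protocol. It is probably small, since sections 3.4 and 12.2 describe hypersensitivity as rare, and it may be zero. Efficacy analyses are unaffected.

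The conclusion rests on reading the baseline visit as all of V1, as the protocol's own wording does, and on the AE tables being drawn from the AE form. An analysis plan written later would not by itself correct what sites had entered.

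**What to change.** Reconcile the vital-signs paragraph of section 11.4 with the AE paragraph and the one-hour monitoring step of the same section, and with section 12.3. Limit the medical-history rule to readings taken before the first injection. State that clinically significant abnormalities measured after the first injection, including the one-hour check at V1, are recorded as AEs with a causality assessment. Replace the reference to visits other than baseline with this time-based split, and carry the same wording into the eCRF guidance.

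For patients already enrolled, query Day 0 medical-history entries before database lock. Ask the site whether each arose from the one-hour reading and, if so, have it entered as an AE. Do this blinded to allocation.

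The cost is one sentence of text and a small data query. No measurement is added and patient management does not change.

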# PHYSICAL EXAMINATION AND INVESTIGATOR ASSESSMENTS

• Modified TLSS (21, 22): The seven individual CHE symptoms; (erythema, scaling, lichenification or hyperkeratosis, vesiculation, edema, fissures, and pruritus/pain) form the composite scale of mTLSS' strength and each one of them scores from 0 (mild) to 3 (severe). The scores are summed, extending from a base estimation of 0 (no signs or symptoms) to the most extreme of 21 (more serious disease).

Symptoms	Severity, morphological description								
erythema	$\Box$ 0 = none								
	□ 1 = mild erythema								
	$\Box$ 2 = redness								
	$\Box$ 3 = deep/dark red erythema								
scaling	$\Box 0 = \text{none}$								
	$\Box$ 1 = mild fines scales, limited area								
	$\Box$ 2 = thicker scales, extended area								
	$\Box$ 3 = thick scales on more than 30% of the hand								
lichenification	$\Box$ 0 = none								
	$\Box$ 1 = mild thickening, limited area								
	$\Box$ 2 = moderate thickening, extended area								
	$\Box$ 3 = severe thickening, extended area								
Skin vesicles	$\Box$ 0 = none								
	$\Box$ 1 = vesicles on less than 10% of the hand								
	$\Box$ 2 = vesicles on 10 to 30% of the hand								
	$\Box$ 3 = vesicle on more than 30% of the hand								
oedema	$\Box$ 0 = none								
	$\Box$ 1 = mild oedema, on less than 10% of the hand								
	$\Box$ 2 = oedema on more than 10% of the hand								
	$\Box$ 3 = oedema and induration on extended area								
cracking	$\Box$ 0 = none								
	$\Box$ 1 = craking on a small part of the hand								
	$\Box$ 2 = painful craking on multiple hand area								
	$\Box$ 3 = deep/dark red erythema								
Pruritus / pain	$\Box$ 0 = none								
	$\Box$ 1 = mild discomfort several times a day								
	$\Box$ 2 = recurring discomfort during the day								
	$\Box$ 3 = persistent discomfort leading to sleep disorder								

Investigator's Global Assessment (IGA): IGA is a global assessment of the patient's overall severity of their CHE, based on a static, numeric 5-point scale from 0 (clear skin) to 4 (severe disease). The score is based on an overall assessment of the degree of erythema, papulation/induration, oozing/crusting, and lichenification. The assessment will be based on the condition of the disease at the time of evaluation and not in relation to the condition at previous visit.

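### In the mTLSS table, level 3 of the cracking item is described by redness, so the top grade of one of the seven primary-endpoint items is wrong as printed

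*Protocol*

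**What the plan says.** Section 10.1 of the Protocol fixes the endpoint: "The primary outcome measure will be the 16-week percent change since baseline of the severity score mTLSS". It describes the score as covering "6 key signs (erythema, desquamation, lichenification/hyperkeratosis, vesiculae, oedema, fissures) and the intensity of pruritus and pain", so redness and fissures are distinct components.

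Section 11.4, under the physical examination and investigator assessments, gives the scoring rule. The lead-in names seven symptoms, with erythema and fissures listed separately. It says "each one of them scores from 0 (mild) to 3 (severe"), and that the items are summed, "to the most extreme of 21 (more serious disease"). The table then describes each level. The cracking row runs:

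- 0: none
- 1: "1 = craking on a small part of the hand"
- 2: "painful craking on multiple hand area"
- 3: "3 = deep/dark red erythema"

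The level 3 words appear twice in the table: once in the erythema row, where they belong, and again in the cracking row. The Protocol gives no other descriptor for severe cracking.

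**The concern.** Levels 1 and 2 of the cracking row grade the extent and painfulness of fissures. Level 3 switches to another sign. It looks like a line copied from the erythema row.

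The table defines the only endpoint that carries a confirmatory test, and the same score at baseline is a covariate in the primary analysis (section 13.4). A rater who takes the row literally can add points for redness that the erythema item has already counted. A rater with a badly fissured but not very red hand finds no matching text above level 2. Other raters will notice the slip and grade by judgement. Section 11.5 makes assessment by the same physician a preference only, so two visits of one patient may be scored on different understandings.

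The trigger is not remote. Section 6.1 admits patients with IGA 3 or 4, and the IGA table in section 11.4 uses the same degree of redness to describe grade 4.

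**Working it through.** **Plan's own figures.** Seven items × 3 = 21, which agrees with the stated maximum. For the sample size (section 13.1: difference 25, SD 40, two-sided 0.05), the exact t-test power is 79.8% with 41 per group and 80.8% with 42, so 84 evaluable patients is reproduced. 84/0.9 = 93.3, rounded up to 94. The defect lies in the measurement and touches none of these figures.

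**Weight of redness.** Intended: at most 3 of 21 points (3/21 = 14.3%). Printed row taken literally: 3 (erythema) + 3 (cracking) = 6 of 21 (28.6%).

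**Effect on one patient's percent change.** Percent change = 100 × (week 16 − baseline)/baseline. The Protocol gives no item-level scores, so these are illustrations. Let O be the sum of the other five items, assumed constant over time at 6, 8 or 10. The intended scoring reads level 3 as severe fissuring. The literal scoring gives cracking 3 whenever redness is at its top grade, and otherwise caps cracking at 2.

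- (a) No fissures, erythema 3 to 0. Intended: O+3 to O. Literal: O+6 to O.
- (b) Fissures at level 2 throughout, erythema 3 to 1. Intended: O+5 to O+3. Literal: O+6 to O+3.
- (c) Severe fissures clear, erythema 1 throughout. Intended: O+4 to O+1. Literal: O+3 to O+1.

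| Case | O | Intended | Literal | Shift in improvement (points) |
|---|---|---|---|---|
| a | 6 | 9 to 6, −33.3% | 12 to 6, −50.0% | 16.7 overstated |
| a | 8 | 11 to 8, −27.3% | 14 to 8, −42.9% | 15.6 overstated |
| a | 10 | 13 to 10, −23.1% | 16 to 10, −37.5% | 14.4 overstated |
| b | 6 | 11 to 9, −18.2% | 12 to 9, −25.0% | 6.8 overstated |
| b | 8 | 13 to 11, −15.4% | 14 to 11, −21.4% | 6.0 overstated |
| b | 10 | 15 to 13, −13.3% | 16 to 13, −18.8% | 5.4 overstated |
| c | 6 | 10 to 7, −30.0% | 9 to 7, −22.2% | 7.8 understated |
| c | 8 | 12 to 9, −25.0% | 11 to 9, −18.2% | 6.8 understated |
| c | 10 | 14 to 11, −21.4% | 13 to 11, −15.4% | 6.0 understated |

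The shift is about 5 to 17 points for an affected patient. It overstates improvement where redness fades, and understates it (by about 6 to 8 points here) where severe fissures heal.

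**The case against.** Several stronger readings are tempting, and the Protocol does not support them.

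- *Severe fissures cannot be scored.* The lead-in lists fissures as an item running up to severe at 3, and cites the source instrument. A specialist rater can give 3 by judgement. What is missing is a correct descriptor.
- *Erythema is counted twice.* A red hand without fissures also meets level 0 of the cracking row, so the form is ambiguous and does not dictate a 3. Double counting happens only if the row is applied literally. The raters are dermatologists or allergologists in referral centres, and many may not do so.
- *The individual shifts can be set against the planned 25-point difference.* That figure is a difference in group means. The shifts belong to hypothetical patients, go both ways, and come with no frequency. They say nothing about how far the group contrast moves.
- *The error biases the test.* Patient and investigator are blinded (section 8.3.1), so the same faulty text applies to both arms. If the drug had no effect, the misread score would be distributed alike in the two groups.

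Two uncertainties also stand. The eCRF, worksheet and rater instructions are not in the document, and they may carry the right text. The table was also read by machine, so the page itself should be checked. A reading artefact is unlikely, since the row has four levels in sequence and the next row starts cleanly.

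None of this removes the contradiction in the printed scoring rule.

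**Conclusion.** The point holds as an error in a stated scoring rule for the primary endpoint. Level 3 of cracking carries the erythema text, contrary to section 10.1 and to the lead-in of the table itself. The consequence is a loss of validity in one of seven items and probable disagreement between raters, hence extra noise in both the baseline and the week 16 score.

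Taken literally, the row doubles the maximum weight of redness from 3 to 6 of 21 points. An affected patient's percent change moves by roughly 5 to 17 points. That range rests on the assumed item scores above and on literal use of the table. How many patients are affected, and the net effect on the treatment difference, cannot be derived from the Protocol. Type I error is not inflated by this alone, and the sample size is unaffected.

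The label mild for level 0 in the lead-in is a trivial slip. Every row of the table defines 0 as none, and the lead-in describes a total of 0 as the absence of signs and symptoms.

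**What to change.** 1. Replace the level 3 text of the cracking row with the fissure descriptor of the source instrument that the Protocol cites, and change the lead-in label for 0 to none in the same edit.
2. Establish which wording the eCRF, the worksheet and the rater instructions actually carried. If they were right, a note to that effect closes the matter.
3. If the printed wording was used, document it. Do not change the anchor in a way that scores a patient's baseline under one text and week 16 under another. This is a real risk: the first inclusion was in July 2019, the inclusion period is 54 months, and version 6.0 dates from June 2023, about 47 months in.
4. In that case, pre-specify in the SAP before unblinding a sensitivity analysis of percent change in mTLSS without the cracking item (6 × 3, so range 0 to 18), with the model and population of the primary analysis. Section 13.2 already requires SAP validation before unblinding, so the route exists.

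The cost is a short text correction, a check of study records and, if needed, one more analysis. That analysis discards valid fissure data at levels 0 to 2 and tests a somewhat different score. It should therefore support the primary analysis and not replace it.
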